### Screening and Randomization

Only one incision/laceration will be treated with the IMD. If a subject has more than one incision/laceration, the target wound will be the one with the greatest length (ie, the longest) that meets the study entry criteria. If the length of 2 or more wounds is equal, the investigator can choose either of them to be the target wound.

The incision/laceration will be prepared for closure as per the standard of care at a treating hospital. The investigator will assess the need and perform closure of deep tissue layers as necessary before proceeding with the closure of the last (dermal) layer with the IMD.

All lacerations will first be assessed for the need of deep suturing and/or debridement; this information will be recorded in the electronic case report form (eCRF). Wounds that require debridement and/or deep suturing will be treated according to the local practice of the investigator and only at the time of skin closure will the lacerations be randomized into 1 of the 2 study treatment arms. Wounds that do not require deep suturing and/or debridement will be randomized immediately.

Re-screening is not allowed in the study.

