### Treatment Phase

Use of Dermabond Advance will be according to Instructions for Use (Section 15.2). Wounds closed with Dermabond Advanced will be prepared in a standard manner. They will be cleaned with an antiseptic solution (which will be recorded in the eCRF), patted dry with dry, sterile gauze, and hemostasis will need to be achieved prior to wound closure (eg, by pressure application or use of local vasoconstrictors). Wound edges will be approximated by fingers of forceps and Dermabond Advanced will be applied in one continuous layer onto a dry wound through painting motions, taking care not to apply adhesive between the wound edges. Applying a second layer is not required or recommended. If a second layer of Dermabond Advanced is applied, or if large droplets of liquid are not spread thinly, the subject may experience an increased sensation of heat or discomfort. The wound will be held for 60 seconds to allow for complete polymerization. The wound may or may not be covered with a protective dressing thereafter.

Wounds closed with MAR-CUTIS will be prepared in a standard manner. They will be cleansed with an antiseptic solution (which will be recorded in the eCRF), patted dry with dry, sterile gauze, and hemostasis will need to be achieved prior to wound closure (eg, by pressure application or use of local vasoconstrictors). The use of peroxide-containing antiseptics is not recommended to be applied directly on the MAR-CUTIS strip as they may provoke cracking of the strip. These products however may be used for preparing the wound for closure. In addition, iodine-containing products may be used as necessary but they may stain the glue strip making it non-transparent. Wound edges will be approximated by fingers of forceps and MAR-CUTIS will be applied in one 1 to 2 mm thick layer ensuring that at least 1 cm of the glue is applied over the length of the wound on each side. The amount of the glue applied will be calculated such that one 5-mL syringe covers up to 8 cm of wound length (giving a total of 10 cm per syringe). For wounds >8 cm, 2 syringes will be needed. The wound will be held for approximately 30 seconds to allow for initial polymerization. Only for the pediatric population, the maximum number of syringes per day is limited based on the body weight as shown in the table below:

Body Weight	Number of MAR-CUTIS Syringes
10 to <15 kg	Maximum of 1 syringe
15 kg and above	Maximum of 2 syringes

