#### **7.3.2 Inclusion Criteria**

For subjects with surgical incisions:

- 
1. Subject undergoing closure of surgical incision  $\geq 6$  to  $\leq 15$  cm following a laparotomy, abdominal hysterectomy, inguinal hernia repair, or laparoscopic intervention.

For subjects with lacerations:

2. Subject requiring closure of a laceration on face (avoiding the immediate area around the eye or lips/mouth) or extremities,  $\leq 15$  cm. In subjects with multiple lacerations, one will be selected as the target wound (ie, greatest length and meets the study entry criteria).

For all subjects:

3. Subject has the ability to consent and has given written informed consent/assent to participate.
4. Male and female subjects  $\geq 2$  years of age and body weight  $\geq 10$  kg.
5. Subject willing and capable of following instructions for wound care provided by the investigator and agreeing to return for all treatment control visits specified in this clinical study.

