### 7.4.5 Application in the Study

Detailed instruction and a training video on the application of MAR-CUTIS will be provided to each investigational site. MAR-CUTIS will be applied in one 1 to 2 mm thick layer, ensuring that at least 1 cm of the glue is applied over the length of the wound on each side.

---

The amount of the glue applied will be calculated such that one 5-mL syringe covers approximately 8 cm of wound length (giving a total of 10 cm per syringe). For wounds >8 cm, 2 syringes will be required. The wound will be held for approximately 30 seconds to allow for initial polymerization. Only for the pediatric population, the maximum number of syringes per day is limited based on the body weight as shown in the table below:

Body Weight	Number of MAR-CUTIS Syringes
10 to <15 kg	Maximum of 1 syringe
15 kg and above	Maximum of 2 syringes

Detailed instruction and a training video on Dermabond Advanced application will also be provided to each investigational site. Use of Dermabond Advanced will be according to Instructions for Use (Section 15.2). Dermabond Advanced will be applied in one continuous layer onto a dry wound through painting motions, taking care not to apply adhesive between the wound edges. Applying a second layer is not required or recommended. If a second layer of Dermabond Advanced is applied or if large droplets of liquid are not spread thinly, the subject may experience an increased sensation of heat or discomfort. The wound will be held for 60 seconds to allow for complete polymerization.

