#### **7.4.6 Timing of Application for Each Subject**

The IMD will be applied only on Day 0 as instructed in Section 7.4.5.

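### Children of 10 to <15 kg are capped at one MAR-CUTIS syringe, yet may enter with wounds over 8 cm that the protocol says need two

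*Protocol*

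**What the plan says.** Section 7.2.1 (Treatment Phase) sets the amount of MAR-CUTIS by wound length: "one 5-mL syringe covers up to 8 cm of wound length (giving a total of 10 cm per syringe"), and then "For wounds >8 cm, 2 syringes will be needed". The glue must extend at least 1 cm past the wound on each side. The same section limits syringes in children by weight. The table entry for 10 to <15 kg is "Maximum of 1 syringe", and from 15 kg upward the limit is two.

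Section 7.4.5 repeats both rules: "For wounds >8 cm, 2 syringes will be required", and for children "the maximum number of syringes per day is limited based on the body weight". Its one difference is that it gives the 8 cm coverage per syringe as approximate.

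Section 7.4.6 fixes the timing: "The IMD will be applied only on Day 0 as instructed in Section 7.4.5".

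Inclusion criteria 1, 2 and 4 (section 7.3.2, repeated in the Synopsis) admit subjects from 2 years and 10 kg with an incision of 6 to 15 cm or a laceration of up to 15 cm. None of the 16 exclusion criteria in section 7.3.3 ties wound length to weight or age.

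**The concern.** For one weight band, the application rule and the paediatric maximum cannot both be followed across most of the permitted wound lengths. Because the device is applied only on Day 0, a per-day limit cannot be met by giving the second syringe on a later day.

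The protocol does not tell a site what to do with such a child. A site might decline to randomise, apply a shorter strip than specified, close the rest of the wound some other way, or exceed the limit. The first two look most likely, because a specific paediatric maximum would normally be taken to override a general rule. The weight limit applies only to MAR-CUTIS, so if the conflict is noticed after allocation it arises in that arm alone, at the moment of skin closure. Section 10.3 leaves little room to improvise: apart from an immediate hazard, deviations need sponsor agreement and an ethics-approved amendment.

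**Working it through.** **Inputs, all from the protocol**

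- Strip per syringe: 10 cm (7.2.1, Treatment Phase).
- Overlap: at least 1 cm on each side, taken as 2 cm in total along the length (7.2.1, 7.4.5).
- Limit at 10 to <15 kg: 1 syringe. Limit from 15 kg: 2 syringes (7.2.1, 7.4.5).
- Longest eligible wound: 15 cm. Shortest eligible incision: 6 cm (7.3.2).
- Planned subjects aged 2 to 21: about 30, of whom about 5 are aged 15 to <22 (7.2.1, Study Design).

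**Reproducing the plan's own threshold**

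Wound length covered by *k* syringes = 10*k* − 2 cm.

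- One syringe: 10 − 2 = 8 cm, which matches the protocol's figure.
- Two syringes: 20 − 2 = 18 cm, which exceeds the 15 cm maximum. Subjects of 15 kg and above are therefore not affected.

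**Applying it to the 10 to <15 kg band**

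Strip needed = wound + 2 cm. Syringes = strip / 10. Share supplied by one syringe = 10 / strip, with a maximum of 100%.

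| Wound (cm) | Strip (cm) | Syringes by length | Share from one syringe |
|---|---|---|---|
| 8 | 10 | 1.0 | 100% |
| 10 | 12 | 1.2 | 83% |
| 12 | 14 | 1.4 | 71% |
| 15 | 17 | 1.7 | 59% |

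The shares are nominal, because they take 10 cm per syringe as fixed.

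For incisions, the conflict covers 15 − 8 = 7 cm of the 15 − 6 = 9 cm permitted range, or 78%. This is a share of the length range and not of subjects.

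**How many children**

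The documents do not give the number. A loose ceiling is 30 − 5 = 25 subjects under 15 years, with 25 × 2/3 ≈ 17 on MAR-CUTIS. That counts every such child whatever the weight or wound length. Only those below 15 kg with a wound over 8 cm are affected, so the range is 0 to about 17, very probably near the low end.

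**The case against.** The textual conflict is not in dispute. The case on the other side is that it hardly matters.

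- **Precedence.** The paediatric maximum follows the general rule in the same section and reads as a limit on it, so over-exposure is unlikely. This is fair. It still leaves the remainder of the wound with no specified closure.
- **Timing.** The Synopsis places final eligibility before allocation on Day 0, so a site can see the weight and wound length and decline. It can see them, but no criterion makes the child ineligible. Declining would be an ad hoc decision.
- **Rarity.** A child of at least 2 years, under 15 kg, with a wound over 8 cm from one of the listed operations or a permitted laceration, is unusual. The affected group may be empty, and the figure of 17 says little about its size. This stands, and it is the main reason the point is minor.
- **Strip length is elastic.** The layer may be 1 to 2 mm thick. Assuming a strip 2 cm wide and no loss in the mixing cannula (neither is stated), 5 mL gives 5 / (2 × 0.2) = 12.5 cm at 2 mm and 5 / (2 × 0.1) = 25 cm at 1 mm. A 17 cm strip would then need 5 / (2 × 17) = 0.147 cm, about 1.5 mm. So a shortened strip is not inevitable and the percentages above are nominal. The written requirement for two syringes above 8 cm is unchanged by this.
- **Other material.** The site instructions, training video or Investigator's Brochure may deal with it. They are not among the documents, and they would not amend the eligibility criteria.

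**Conclusion.** The concern holds and is minor. An eligible child of 10 to <15 kg with a wound of more than 8 and up to 15 cm, if allocated to MAR-CUTIS, cannot be treated within both stated rules. Close to 8 cm the boundary is soft, because section 7.4.5 calls the coverage approximate. At 15 cm the conflict is plain.

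The conclusion rests on the protocol's own coverage rule and on reading the 1 cm overlap as applying at each end of the wound, the reading that reproduces the 8 cm threshold. It does not depend on the significance level, margin, event rates or sample size. The likely consequences are unplanned non-enrolment or a strip shorter than specified in very few children, possibly none, with no material effect on power or the primary analysis.

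**What to change.** Add one line to the inclusion criteria in the Synopsis and section 7.3.2: *For subjects weighing 10 to <15 kg, the target wound must be ≤8 cm.* Apply it to both arms and check it before randomisation, so that exclusion cannot depend on the allocated device.

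Incisions of 6 to 8 cm and lacerations of up to 8 cm stay open to this weight band. The rule for subjects with several wounds needs no edit: since "the target wound will be the one with the greatest length (ie, the longest) that meets the study entry criteria", it would pick the longest wound within the new limit. Nothing changes from 15 kg upward.

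The cost is one line in two places and one pre-randomisation check. Weight and wound length are already entry criteria, so no new data are needed. The downside is that a few small children with wounds over 8 cm could not enrol. Those are children whom the protocol cannot treat as specified if they are allocated to MAR-CUTIS. A sentence in section 7.4.5 saying how to close such wounds would also remove the contradiction, but the sponsor would have to define a closure method for the part of the wound not covered.

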### **7.3 Selection of Study Population**

The study population will include subjects with surgical incisions from  $\geq 6$  to  $\leq 15$  cm or lacerations  $\leq 15$  cm who meet the criteria specified below.

#### **7.3.1 Number of Planned Subjects**

A total of 189 subjects will be treated (defined as study product applied to the wound). Only subjects that are withdrawn from the study due to product failure at the time of application (see Section 7.3.4) will be replaced.

#### **7.3.2 Inclusion Criteria**

For subjects with surgical incisions:

- 
1. Subject undergoing closure of surgical incision  $\geq 6$  to  $\leq 15$  cm following a laparotomy, abdominal hysterectomy, inguinal hernia repair, or laparoscopic intervention.

For subjects with lacerations:

2. Subject requiring closure of a laceration on face (avoiding the immediate area around the eye or lips/mouth) or extremities,  $\leq 15$  cm. In subjects with multiple lacerations, one will be selected as the target wound (ie, greatest length and meets the study entry criteria).

For all subjects:

3. Subject has the ability to consent and has given written informed consent/assent to participate.
4. Male and female subjects  $\geq 2$  years of age and body weight  $\geq 10$  kg.
5. Subject willing and capable of following instructions for wound care provided by the investigator and agreeing to return for all treatment control visits specified in this clinical study.

### 7.3.3 Exclusion Criteria

Subjects will be excluded from the study if one or more of the following criterion is applicable:

For subjects with lacerations:

1. Wounds on mucosal surfaces or across mucocutaneous junctions (eg, oral cavity, lips, eyes).
2. Wounds which may be regularly exposed to body fluids or with dense natural hair (eg, scalp); wounds on ears.
3. Wounds on palms and feet.
4. Animal or human bites.
5. Lacerations that are heavily contaminated.
6. Punctured or crushed wounds.
7. Subjects with lacerations having wound treatment  $> 6$  hours after the trauma.

For all subjects:

8. Subjects requiring suturing with sutures  $> 0.5$  mm thickness.
9. Subject with documented skin disease or skin conditions (eg, excessive hair at the site of surgery, scar tissue, wound, tattoo, coloration, or pre-existing open sores at the site of surgery that would interfere with the application of IMD or the skin assessment, as judged by the investigator).
10. Subject with any factors that may have an adverse effect on wound healing (eg, previous history of keloid formation or hypertrophy [including family history]), other general risk factors for dehiscence (need of premature post-surgery exercise/heavy

---

lifting, expected conditions leading to recurrent vomiting, coughing, or constipation), history of immunosuppression, chronic systemic infection, or poor general health.

11. Subjects with known blood clotting disorders.
12. Subjects receiving chronic, pre-operative steroids, immunosuppressants, chemotherapy, or anticoagulants; only chronic anti-platelet therapies like acetylsalicylic acid (ASA) and clopidogrel are accepted. Chronic is to be interpreted as long term or “for more than acute treatment”. Pre-operative standard of care, like a single dose of an anticoagulant, for the aforementioned treatments is allowed along with standard of care post-operative anticoagulant and chemotherapy regimen including application of steroids and immunosuppressants.
13. Subject having known or suspected allergy or sensitivity to polyurethane, cyanoacrylates, formaldehyde, tapes or adhesives, or benzalkonium chloride.
14. Subject participating in any current clinical study with a non-Conformité Européenne–marked device or investigational product.
15. Subject who is pregnant or breastfeeding.
16. Subject with history of a significant dermatologic disease or condition, such as atopic dermatitis, psoriasis, lichen ruber planus, vitiligo or conditions known to alter the skin appearance or physiologic response (eg, decompensated diabetes mellitus, porphyria) that involves the investigative site.

#### **7.3.4 Removal of Subjects From Therapy or Assessments**

Subjects may stop the study for any of the following reasons:

- Subject request
- Use of nonpermitted concurrent therapy
- Lost to follow-up (considered lost to follow-up only before Day 10)
- Occurrence of AEs not compatible with the continuation of subject participation in the study, in the investigator’s opinion, or unacceptable to the subject to continue
- Investigator request
- Intercurrent illness

Subjects are free to withdraw from the study at any time without providing reason(s) for withdrawal and without prejudice to further treatment. The reason(s) for withdrawal will be documented in the eCRF.

Subjects withdrawing from the study will be encouraged to complete the same final evaluations as subjects completing the study according to this protocol, particularly safety evaluations. The aim is to record data in the same way as for subjects who completed the study.

Reasonable efforts will be made to contact subjects who are lost to follow-up. These efforts must be documented in the subject’s file.

---

The sponsor has the right to terminate the study at any time in case of SAEs or if special circumstances concerning the IMD or the company itself occur, making further treatment of subjects impossible. In this event, the investigator(s) will be informed of the reason for study termination.

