## 6 STUDY OBJECTIVES

Objectives	Endpoints

Primary Efficacy Objective:
 
 
To compare the dehiscence rate between MAR-CUTIS and Dermabond Advanced between Day 1 and Day 10.
 
	
Primary Efficacy Endpoint:
 
 
Total dehiscence rate of target incision/laceration assessed at the Day 10 visit.
 

Main safety objective:
 
 
To compare the incidence of AEs between MAR-CUTIS and Dermabond Advanced.
 
	
Main safety endpoint:
 
 
Adverse events within 1 month after treatment classified by severity and relatedness to the treatment.
 

Secondary
	

 
To compare the dehiscence rate between MAR-CUTIS and Dermabond Advanced at the Month 1 visit.
 
	
 
Total dehiscence rate of target incision/laceration assessed at the Month 1 or Early Discontinuation visit (if Early Discontinuation occurs before Month 1).
 

 
To compare the incidence of AEs between MAR-CUTIS and Dermabond Advanced at additional study time points.
 
	
 
Adverse events classified by severity and relatedness to the treatment.
 

 
To evaluate the subject satisfaction with the cosmetic outcome after treatment of the surgical incision/laceration with MAR-CUTIS versus Dermabond Advanced.
 
	
 
Subject-completed Patient and Observer Scar Assessment Scale (POSAS) done at the Month 1 and Month 3 visits or at the Early Discontinuation visit (if Early Discontinuation occurs before Month 1).
 

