### **9.3.2.3 Follow-up of Adverse Events**

All investigators should follow-up with subjects with AEs/ADEs/SAEs until the event is resolved or until, in the opinion of the investigator, the event is stabilized or determined to be chronic. Details of AE resolution must be documented in the eCRF. If the AE extends beyond the end of the study, it will be followed until resolution although the study will proceed with close-out activities independently.

Subjects should be followed-up by the end of study visit (Month 3/Early Discontinuation), and any AEs/ADEs/SAEs/DDs that occur during this time should be reported according to the procedures outlined above.

For all SAEs, where important or relevant information is missing, active follow-up should be undertaken. The subject must be followed-up until clinical recovery is complete and laboratory results have returned to normal, or until progression has been stabilized or until the last study visit, whichever comes first. This information should be documented in the subject's medical records.

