### **10.1.5 Handling of Missing Data**

For the primary endpoint main analysis on the FAS population, any missing data for the primary endpoint will be handled as outlined in the following:

- 
- Subjects with a provided reason for not attending the Day 10 Visit related to problems with the wound closure will be counted as a failure (ie, the subject experiences a dehiscence)
  - Subjects with a dehiscence experienced and recorded before the Day 10 Visit (Day 1 or unscheduled visit) will be counted as a failure (ie, the subject experiences a dehiscence)
  - All other subjects (eg, lost to follow-up with no dehiscence before) will be counted as success (ie, the subject experiences no dehiscence up to Day 10 for the primary endpoint analysis), since it is expected that subjects with problems of wound closure will attend the Day 10 visit to see the investigator and assess the wound status, and given the very low expected rate of dehiscence

In any case, all efforts will be made to contact subjects not attending Day 10 visit to gain information about the reason for nonattendance and about potential dehiscence.

Further information on how to treat missing data for other variables will be given in the SAP.

---

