8 ANALYSIS CONVENTIONS

8.1 General principles

If two of the analysis sets as defined in the SAP coincide, presentations will only be prepared for one analysis set.

All presentations will be done by treatment group and overall, and by visit where applicable.

The data collected and derived in the trial will be presented in subject data listings sorted by subject number and treatment.

Data collected in this trial will be summarized according to their nature as follows:

- Continuous variables: number of non-missing observations, arithmetic mean, standard deviation (SD), minimum (Min) and maximum (Max) values, median, and first (Q1) and third (Q3) quartiles. If there are less than 5 observations, descriptive statistics will be presented based on the rules specified in Section 16.1.1.2.
- Categorical variables: absolute and relative frequencies. If not defined otherwise, the percentage denominator will be the number of subjects still in the trial (including missing values) at the respective time point in the analysis set. The category missing will only be displayed if missing values occur. Categories with a frequency of 0 will not be presented if not otherwise specified.

Medical terms (e.g., prior and concomitant diseases, adverse events) will be coded via Medical Dictionary for Regulatory Activities (MedDRA) version 21.0 or latest version before the database is locked. For the analysis, the primary System Organ Class (SOC) will be used. Medications will be coded according to World Health Organization Drug Dictionary (WHO-DD) version March 2018 or latest version before the database is locked.

Shells for summary tables, subject listings, and figures are described in a separate document, which is included as an Appendix to the SAP. Templates for each unique table, listing, and figure are provided. These provide only a draft indication of the content and appearance of the tables, listings, and figures, and the final output may vary in appearance from these templates.

All statistical analyses will be performed using SAS statistical software version 9.4 or higher (SAS Institute, Cary, NC).

[Table 1](#) shows the use of analysis sets in different analyses as defined in Section 9.

Table 1: Use of analysis sets

	Enrolled Set	Allocated Set	SAF	FAS
Subject disposition	X	X		
Discontinuations			X	
Protocol deviations			X	
Demographics			X	X
Other baseline characteristics			X	X
Subject medical history			X	
Previous and concomitant medication			X	
Exposure			X	

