16.1.1.7 Handling of missing values

At each time point/visit, all subjects still in the trial (i.e., subjects who have not been withdrawn from the study) are reported. Missing values will be taken into account as missing in the analysis, unless specified differently (e.g., primary efficacy analysis). The number of observed values and the number of missing values must add up to the number of subjects in the trial at the respective time point/visit.

Unless otherwise specified in the SAP, missing values will not be imputed (with the sole exception of primary efficacy data, as discussed in Section 13.1.1). If missing values are imputed, the result of all imputation strategies and newly derived information must be stored in the ADaM data set.

Imputed values will be listed in the subject data listing and marked as imputed.

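### Protocol 7.3.4 ends loss to follow-up at Day 10, so a subject without a known AE who stops attending later has no tracing rule, although safety follow-up runs to Month 3

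*Protocol*

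**What the plan says.** Among the reasons for stopping, Protocol 7.3.4 gives "Lost to follow-up (considered lost to follow-up only before Day 10". The same section then says "Reasonable efforts will be made to contact subjects who are lost to follow-up", and requires these efforts to be documented.

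The other rules on contacting non-attenders concern early visits. Protocol 8.2 provides for a telephone contact when a laceration subject misses Day 1 and, exceptionally, when any subject misses Day 10. Protocol 10.1.5 adds that "all efforts will be made to contact subjects not attending Day 10 visit", and SAP 13.1.1 repeats this.

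Safety follow-up lasts much longer. The main safety endpoint in Protocol 6 is "Adverse events within 1 month after treatment classified by severity and relatedness to the treatment". Wound infection is assessed at Day 10, Month 1 and Month 3. Protocol 9.3.2.3 states "Subjects should be followed-up by the end of study visit (Month 3/Early Discontinuation), and any AEs/ADEs/SAEs/DDs that occur during this time should be reported".

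For categorical by-visit summaries, SAP 8.1 says that, unless defined otherwise, "the percentage denominator will be the number of subjects still in the trial (including missing values) at the respective time point". SAP 16.1.1.7 explains the term: "all subjects still in the trial (i.e., subjects who have not been withdrawn from the study) are reported". SAP 13.2.3.2 sets each infection-score item to 0 when it is not recorded or is missing.

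**The concern.** The cut-off suits the primary endpoint, which closes at the Day 10 visit. It does not suit the other endpoints. Someone who attends on Day 10 and never returns is, by this wording, not lost to follow-up, so the contact sentence does not reach that person. No other stopping reason in 7.3.4 plainly describes silent non-attendance.

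What is at stake is the completeness of the later safety data. The protocol's own infection criteria (Protocol 15.1) use a 30-day surveillance period for superficial infection and a 90-day period for herniorrhaphy, and inguinal hernia repair is an eligible procedure. A contact that is not attempted during the trial cannot be recovered at analysis. In an open-label trial the loss could also differ between arms.

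**Working it through.** **1. The plan's own figures.** The documents give no loss rate and no dropout allowance, so there is no stated figure to reproduce on this point. As a check on the design inputs, exact enumeration of the Farrington-Manning test (126 versus 63 subjects, 3.05% versus 0.85%, margin 8%, one-sided 0.05) gives 85.8% power against the stated 85%. That endpoint closes at Day 10, so a rule about later loss does not enter it.

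**2. Contact rules by visit.**

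| Missed visit | Specific rule for contacting a non-attender |
|---|---|
| Day 1 | Telephone, laceration subjects (Protocol 8.2) |
| Day 10 | Telephone and all efforts (Protocol 8.2, 10.1.5; SAP 13.1.1) |
| Month 1 | None |
| Month 3 | None |

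Protocol 9.3.2.3 does apply after Day 10. It requires follow-up to the final visit, follow-up of subjects with known events, and active pursuit of missing information on serious events. It gives no step for tracing a subject without a known event.

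**3. Adverse event tables.** The Safety Set (SAP 9.3) is everyone in whom application started. The overview percentages (SAP 14.1) and the crude incidence rate (SAP 14.1.1) divide by all such subjects in the group. A subject lost on Day 3 and one lost on Day 20 both stay in the denominator, whatever the label.

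Loss itself does lower these rates. Take a true 30-day risk p and a share L that vanishes at Day 10, with constant hazard:

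- risk by Day 10 = 1 − (1 − p)^(10/30)
- observed rate = (1 − L)p + L × (risk by Day 10)

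With p = 11.5% (allergic reactions with other adhesives, Protocol 5), the Day 10 risk is 1 − 0.885^(1/3) = 4.0%.

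- L = 5% (assumed): 0.95 × 11.5% + 0.05 × 4.0% = 11.1%
- L = 20% (assumed): 0.80 × 11.5% + 0.20 × 4.0% = 10.0%

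Relabelling these subjects changes neither result.

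**4. By-visit infection percentages.** Here the label can matter. A vanished subject who is not recorded as withdrawn counts as still in the trial and stays in the denominator without an assessment. If a share L of N is unassessed and the rate among the assessed is p, the table shows p(1 − L)N / N = p(1 − L).

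Inputs: p = 3.6% (infection with other adhesives, Protocol 5); N = 189; L assumed to be 5% to 15%, which is 189 × 0.05 ≈ 9 to 189 × 0.15 ≈ 28 subjects.

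- L = 5%: 3.6% × 0.95 = 3.4%
- L = 15%: 3.6% × 0.85 = 3.1%

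If those lost have the same 3.6% risk, the unseen infections number 9 × 0.036 = 0.3 to 28 × 0.036 = 1.0. With unequal loss of 20% and 5% (assumed) and the same true rate, the arms would read 3.6% × 0.80 = 2.9% and 3.6% × 0.95 = 3.4%.

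**5. Infection score.** SAP 13.2.3.2 does not exclude a wholly missed visit from the zero rule. If the rule is applied there, the mean score shrinks by the same factor (1 − L), and the missed visit no longer shows as missing.

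**The case against.** The strongest reply is that little follows from an awkward parenthesis. Protocol 9.3.2.3 already obliges sites to follow subjects to Month 3. A withdrawal can be recorded under investigator request, and SAP 10.2 allows for other reasons. Attrition is visible: SAP 8.1 displays a missing category whenever missing values occur, SAP 16.1.1.7 makes observed and missing counts add up at each visit, and SAP 10.1 tabulates completers by arm, who under SAP 8.2.2 must have the Month 3 visit. All endpoints other than the primary are descriptive. The zero rule is also sensible at an attended visit, because Protocol 8.2.2 has the criteria scored only if an infection occurred.

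Most of this stands, and it rules out three stronger readings.

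- A reader might infer that the Day 10 rule keeps vanished subjects in the adverse event denominators and so understates the main safety endpoint. It does not: crude incidence on all treated subjects does that for any loss, early or late.
- A reader might infer that no follow-up duty exists after Day 10. One does; only the tracing step is missing.
- A reader might infer that late attrition is hidden. By-visit missing counts and completer counts show it, though not in the infection score if missed visits are set to 0.

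The reply does not supply a contact rule for missed Month 1 and Month 3 visits. Nor does it say that a vanished subject must be recorded as withdrawn. The available reasons permit that, but no text requires it.

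**Conclusion.** The point holds as a minor defect. After Day 10 the protocol has a follow-up duty but no tracing step for a subject without a known event who stops attending, and it does not say how to classify that subject. The main consequence is avoidable missing safety data between Day 10 and Month 3.

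The numerical effect is confined to by-visit infection results and is at most about half a percentage point (3.6% read as 3.1%). It rests on three assumptions: a loss of 5% to 15%, for which the documents give no basis; an infection rate borrowed from other adhesives; and vanished subjects not being recorded as withdrawn. It would be larger if subjects with complications sought care elsewhere. The primary analysis and its power are unaffected.

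**What to change.** In Protocol 7.3.4:

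- Delete the parenthesis.
- Define a subject as lost to follow-up when he or she returns for no remaining visit through Month 3 and cannot be reached after documented attempts. State that a single missed visit followed by a return is not loss. Otherwise a laceration subject who misses Day 1, or anyone who misses Month 1 but attends Month 3, would be labelled lost.
- Extend the documented contact attempt, including a telephone call about adverse events and wound status, to missed Month 1 and Month 3 visits.

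In the SAP:

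- Show by arm how many subjects have known adverse event status and known infection status at Month 1 and Month 3.
- Base by-visit infection percentages on subjects assessed at that visit.
- Limit the zero rule in 13.2.3.2 to attended visits, so that a wholly missed visit stays missing.

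The cost is a short protocol amendment, occasional calls by existing site staff and a few extra table rows.
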